#### **6.6.4 Disposal and destruction**

The study treatment supply can be destroyed at the local Novartis facility, Drug Supply group or third party, as appropriate.

## **7 Visit schedule and assessments**

### **7.1 Study flow and visit schedule**

Table 7-1 lists all of the assessments and indicates with an “X”, the visits when they are performed. All data obtained from these assessments must be supported in the patient’s source documentation. The table indicates which data are entered into the database (D) or remain in source documents only (S). Assessments that generate data for database entry and which are recorded on eCRFs are listed using the eCRF name.

No CRF will be used as a source document.

**Table 7-1 Visit evaluation schedule**

				Randomized treatment phase			Post Treatment Follow up phase	Survival follow up phase
	Category	Protocol Section	Screening/ Baseline	Cycle 1	Every 2 cycles after C1D1	End of study treatment (EoT)		
Visit Name			Screening Visit (D -21 to D -1)	C1D1	C3D1 C5D1, etc...	EOT Visit (within 7d of last dose)	POST TRT FUP 1, 2, ect	Survival fup
Obtain Informed Consent	D,S		X					
IRT screening / randomization / discontinuation / progression / death	S		X	X		X		
Patient history	D		X					
Demography	D		X					
Inclusion/exclusion criteria	D		X					
Medical History	D		X					
Diagnosis and extent of cancer	D		X					
Smoking history	D		X					
Prior/Post antineoplastic therapy	D		X			X		
Prior/concomitant medications	D		X	Continuous			up to 30 days after last dose of treatment	
Complete Physical examination	S	7.2.2.1.	X	If clinically indicated				
Performance status	D	7.2.2.4.	X	X	X	X		
Height	D	7.2.2.3.	X					
Weight	D	7.2.2.3.	X	X	X	X		
Vital signs	D	7.2.2.2.	X	X	X	X		

				Randomized treatment phase			Post Treatment Follow up phase	Survival follow up phase
	Category	Protocol Section	Screening/ Baseline	Cycle 1	Every 2 cycles after C1D1	End of study treatment (EoT)		
Visit Name			Screening Visit (D -21 to D -1)	C1D1	C3D1 C5D1, etc...	EOT Visit (within 7d of last dose)	POST TRT FUP 1, 2, ect	Survival fup
Laboratory assessments								
Hematology	D	7.2.2.5.1.	X	X	X	X		
Biochemistry	D	7.2.2.5.2.	X	X	X	X		
Lipid Panel	D		X	X	X	X		
Coagulation	D	7.2.2.5.	X	X	X	X		
Hepatitis B and C screening/monitoring(if applicable)	D		X		X	X		
Tumor evaluation ( EOT scan not required if previous scan was performed within ≤28 days)	D	7.2.1.	X		Every 2 cycles after C1D1; the frequency will be changed to every 12 weeks after data cut-off for primary analysis and as clinically indicated	X	X If not progressed, every 2 cycles after EOT ; the frequency will be changed to every 12 weeks after data cut-off for primary analysis and as clinically indicated	
ECG	D	7.2.2.5.3.	X	If clinically indicated				
Pulmonary function test	D			If clinically indicated, and if warranted to exclude or manage non-infection pneumonitis				
Safety								
Adverse events	D		X	Continuous			Up to 30 days after last dose of treatment	
PK blood sampling 	D	7.2.3.	X 1a	X 1,1a				

				Randomized treatment phase			Post Treatment Follow up phase	Survival follow up phase
	Category	Protocol Section	Screening/ Baseline	Cycle 1	Every 2 cycles after C1D1	End of study treatment (EoT)		
Visit Name			Screening Visit (D -21 to D -1)	C1D1	C3D1 C5D1, etc...	EOT Visit (within 7d of last dose)	POST TRT FUP 1, 2, ect	Survival fup
Study treatment administration								
Everolimus / Placebo Dosing	D			Continuous daily dosing				
Exemestane Study Dosing	D			Continuous daily dosing				
Survival Follow-up	D							X every 12 weeks

### **7.1.1 Molecular pre-screening**

Not applicable.

### **7.1.2 Screening**

Written informed consent must be obtained before any study specific assessments are performed, including screening.

The screening assessments must be performed within maximum 21 days to confirm patient's eligibility and to the first study treatment dose of randomized treatment phase.

Laboratory, physical examination, performance status and vital signs assessments should be performed within 7 days before Cycle 1 Day 1.

Tumor evaluation should be performed within 21 days prior to study treatment start in the randomized treatment phase on cycle 1 day 1 except for bone scans as noted below.

As part of patient's routine disease care (prior to signing study inform consent), with proper documentation in patient's file, the following tumor assessments can be used:

- if bone scan was performed within 4 weeks prior cycle 1 day 1

or

- if tumor scans were performed within 21 days prior to cycle 1 day 1.

For laboratory evaluations used to determine eligibility, a repeated evaluation within the screening window is permitted for screening results out of the defined range. If the repeated laboratory result meets the criteria, that result may be used to determine eligibility. If the repeated laboratory result does not meet the criteria, the patient will be considered a screening failure.

Performance status, weight, and vital signs performed  $\leq$  7 days of the first dose of study treatment do not need to be repeated on Day 1 of Cycle 1.

#### **7.1.2.1 Eligibility screening**

Following registering in the IRT for screening, patient eligibility will be checked once all screening procedures are completed. The eligibility check will be embedded in the IRT system. Please refer and comply with detailed guidelines in the IRT manual.

Re-screening is allowed, only, for patients who meet all of the inclusion/exclusion criteria, but were not randomized due to one of the following administrative reasons:

- CT /MRI results have expired (>28 days prior to randomization) due to unexpected administrative issues
- Unexpected drug supply issues.

Procedure for re-screening is as follows:

- Site must register the patient as a screen failure in IRT
- Site is to send a re-screening request to the CRA within 7 days of the screen failure date
- Subject number will be the same as the initial screening

- Informed consent doesn't need to be resigned.
- Lab assessments needs to be performed -7 or -1 days before randomization

Adverse events that begin or worsen after informed consent should be recorded in the Adverse Events CRF. Conditions that were already present at the time of informed consent should be recorded in Medical History CRF.

CRA is to review and confirm patient's eligibility for re-screening with the site.

Patients may be re-screened only once and must be randomized within 28 days after the recorded rescreening date. All evaluations including original assessments and repeated assessments must be collected on the eCRF.

#### **7.1.2.2 Information to be collected on screening failures**

Patients who sign an informed consent but fail to be started on treatment for any reason will be considered a screen failure. The reason for not being started on treatment will be entered on the Screening Phase Disposition Page. The demographic information, informed consent, and Inclusion/Exclusion pages must also be completed for Screen Failure Patients. No other data will be entered into the clinical database for patients who are screen failures, unless the patient experienced a Serious Adverse Event during the Screening Phase (see [Section 8](#) for SAE reporting details). If the patient fails to be randomized, the IRT must be notified within 2 days of the screen fail that the patient was not randomized.

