#### **Randomized treatment phase**

All eligible patients will be randomized within 7 days before Cycle 1 Day 1 to one of the two treatment arms: everolimus plus exemestane arm or placebo plus exemestane arm. Randomization will be stratified according to the presence of visceral disease and sensitivity to prior hormonal therapy status. Visceral refers to lung, liver, brain, pleural and peritoneal involvement. Sensitivity to prior hormonal therapy is defined as either (1) documented clinical benefit (complete response, partial response, stable disease  $\geq$  24 weeks) to at least one prior hormonal therapy in the advanced setting or (2) at least 24 months of adjuvant hormonal therapy prior to recurrence.

Randomized patients will start the study treatment at Cycle 1 Day 1. Patients will receive everolimus/placebo (10 mg daily oral tablets) in addition to exemestane (25 mg daily oral tablets) continuously. Dose adjustment (reduction, interruption) according to safety findings will be allowed ([Section 6.3](#)).

Patients will receive treatment until disease progression (assessed by RECIST 1.1), unacceptable toxicity, death or discontinuation from treatment for any other reason. Tumor assessments will be performed every 8 weeks after randomization until radiological progression per local assessment. Tumor assessments are to be performed every 12 weeks after data cut-off for primary analysis and as clinically indicated, until disease progression.

Imaging data used for tumor assessments during treatment phase and follow-up phase will be centrally collected, checked for quality and reviewed by a central vendor designated by

Novartis. The central review of the scans will be carried out in a blinded fashion. The decision regarding patient management will remain with the local investigator.

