## 6.5      Patient numbering, treatment assignment or randomization

### 6.5.1      Patient numbering

Each patient is identified in the study by a Subject number, that is assigned when the patient is first enrolled for screening and is retained as the primary identifier for the patient throughout his/her entire participation in the trial. The Subject number consists of the Center Number (Center No.) which is assigned by Novartis to the investigative site with a sequential patient number suffixed to it, so that each subject is numbered uniquely across the entire database. Upon signing the informed consent form, the patient is assigned to the next sequential Subject number available to the investigator.

The investigator or designated staff will contact the IRT and provide the requested identifying information for the patient to register them into the IRT. Once assigned, the Subject number must not be reused for any other subject and the Subject number for that individual must not be changed, even if the patient is re-screened. If the patient fails to be randomized or start treatment for any reason, the reason will be entered into the Screening Disposition page.

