## **10.1 Analysis sets**

### **10.1.1 Full Analysis Set**

The Full Analysis Set (FAS) comprises all patients to whom study treatment has been assigned by randomization. According to the intent to treat principle, patients will be analyzed according to the treatment and strata they have been assigned to during the randomization procedure.

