2.2 Analysis sets

The Full Analysis Set (FAS) comprises all subjects to whom study treatment has been assigned by randomization. According to the intent to treat principle, subjects will be analyzed according to the treatment and strata they have been assigned to during the randomization procedure.

The Safety Set (SAF) consists of all subjects who received at least one dose of study treatment. Subjects will be analyzed according to treatment actually received, where treatment received is defined as the randomized treatment if the subject took at least one dose of that treatment or the first treatment received if the randomized treatment was never received.

The actual treatment received corresponds to:

- the randomized treatment if subjects took at least one dose of that treatment
- the first treatment received if the randomized treatment was never received

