2.3 Subject disposition, demographics and other baseline characteristics

Subjects who sign an informed consent but fail to be started on treatment for any reason will be considered a screen failure. The reason for not being started on treatment will be entered on the Screening Phase Disposition Page. The demographic information, informed consent, and Inclusion/Exclusion pages must also be completed for Screen Failure Subjects. A summary of the demographic, baseline disease characteristics and prior antineoplastic therapy of the study population was provided in the primary CSR [Study Y2202-Section 10.4].

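### As worded, the screen-failure rule also takes in randomised, never-dosed patients and stops their data entry, against the all-randomised FAS, and SAP 2.1.9 gives OS no randomisation-date fallback

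*Protocol*

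**What the plan says.** Protocol 7.1.2.2 defines a screen failure by whether treatment was started, not by whether the patient was randomised: "Patients who sign an informed consent but fail to be started on treatment for any reason will be considered a screen failure". Demography, consent, inclusion/exclusion and disposition pages are completed. Beyond those, "No other data will be entered into the clinical database for patients who are screen failures", with one exception for an SAE during the screening phase.

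Two other places use the same trigger without the data restriction:

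- Protocol 6.5.1: "If the patient fails to be randomized or start treatment for any reason, the reason will be entered into the Screening Disposition page".
- SAP 2.3: "Subjects who sign an informed consent but fail to be started on treatment for any reason will be considered a screen failure".

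Protocol 4.1 opens the gap in which a patient can be randomised and not dosed: "All eligible patients will be randomized within 7 days before Cycle 1 Day 1".

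The analysis population has no dosing condition. The FAS in protocol 10.1.1 "comprises all patients to whom study treatment has been assigned by randomization", and in SAP 2.2 it "comprises all subjects to whom study treatment has been assigned by randomization". Protocol Table 7-2 schedules imaging every 8 weeks from randomisation, and the post-baseline imaging text in 7.2.1 applies that schedule whatever the actual dosing. Protocol 4.1 and 7.1.6.3 follow all patients for survival. SAP 2.5.1 uses all data observed in FAS subjects.

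**The concern.** The same patient falls under two incompatible instructions. One treats her as a screening record with almost no data. The others treat her as a full member of the intention-to-treat population, with scans and survival follow-up.

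A site that followed 7.1.2.2 would remove post-randomisation information from a randomised patient for a reason that arises after randomisation. That is what an all-randomised analysis is meant to prevent. This SAP governs the final PFS analysis and the only OS analysis (SAP 2.5.2 and 2.7), so both would carry a patient with no follow-up. For OS, the SAP would not say where to censor her.

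**Working it through.** **1. Does the definition reach a randomised patient?** It requires consent and failure to start treatment for any reason. A patient randomised, say, 5 days before Cycle 1 Day 1 who never takes a tablet meets both conditions. Protocol 6.5.1 names not being randomised and not starting treatment as alternatives, so the second is a trigger in its own right. Protocol 7.1.6.2 does not bring her back, because it words off-treatment tumour follow-up for patients who discontinued treatment.

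**2. PFS if 7.1.2.2 is obeyed.** There is no post-baseline scan. Appendix 1 (14.1.3.2.8 and 14.1.4.5.1) then uses the randomisation date, giving a duration of 1 day. PFS is defined, but the patient contributes nothing to the hazard ratio.

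**3. OS if 7.1.2.2 is obeyed.** SAP 2.7 censors at the last contact date. SAP Table 2-1 lists nine sources:

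- Eight are closed by the data restriction: survival follow-up page, further antineoplastic therapy, dosing record, end-of-treatment page, tumour assessment, laboratory, vital signs and performance status.
- The ninth, AE dates, is open only for a screening-phase SAE. Such a date helps only if it falls on or after randomisation, a window of at most about 7 days.

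The randomisation date is not listed. Appendix 1 (14.1.3.2.8) falls back to the end-of-treatment visit, which protocol Table 7-1 ties to the last dose. The restriction would also stop a death from being entered.

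**4. Size. The plan's own figures first.** Inputs from protocol 10.6: control median 4.1 months, HR 0.62, 110 events, 160 patients 1:1, 18 months' uniform accrual (A), analysis at about 22 months (T), 10% loss.

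- 90% CI = HR × exp(±1.645 × 2/√d). For d = 110 the half-width on the log scale is 3.290/10.488 = 0.314, giving 0.453 to 0.848. The protocol states 0.45 to 0.85.
- Event probability per arm = 1 − [exp(−λ(T−A)) − exp(−λT)]/(λA), with λ = ln 2/median. This gives 0.841 (control) and 0.704 (everolimus), mean 0.773. Required N = 110/0.773/0.9 ≈ 158, against about 160 stated.

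**5. Effect of never-dosed patients.** The documents give no count. Assume 1% to 3% of 160, about 2 to 5 patients.

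- Expected events at 22 months with flat 10% loss: 160 × 0.9 × 0.773 = 111.3. If 2 patients contribute none, 109.9; if 5, 107.8.
- Precision: 5 patients cost 5 × 110/160 = 3.4 events. With d = 106.6 the 90% CI is 0.451 to 0.853.
- Point estimate: simulated trials with 80 per arm, cut at the 110th event, exponential loss, unstratified Cox model, and never-dosed patients given the control hazard in either arm. Full follow-up is compared with day-1 censoring.

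| Never-dosed (everolimus + placebo) | Full follow-up HR | Day-1 censored HR | Shift |
|---|---|---|---|
| 1 + 1 | 0.6227 | 0.6189 | 0.004 |
| 2 + 3 | 0.6244 | 0.6167 | 0.008 |
| 3 + 2 | 0.6305 | 0.6190 | 0.012 |

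The shift favours everolimus in each case, but it is small beside an interval running from about 0.45 to 0.85.

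**The case against.** The strongest reply is that the context shows what was meant. Section 7.1.2.2 sits under Screening, uses a screening-phase disposition page and ends with an IRT notice for patients who were not randomised. Section 7.1.2.1 applies screen-failure registration to patients who met the criteria "but were not randomized due to one of the following administrative reasons", and it still requires their evaluations on the eCRF, so the restriction is not absolute even there. The imaging and survival sections are more specific about randomised patients. If sites follow those, nothing is lost and the OS date is defined. All of this stands, and it is why the point is minor. It does not cure the wording, because no section exempts randomised patients.

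A second reply is that the sponsor receives randomisation data through IRT (protocol 9.3 and 9.4), so the date is always to hand. That is true, and it makes the fallback easy to add. SAP Table 2-1 still does not use it.

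A reader might infer more than the documents support:

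- **That three sections bar the data.** Only protocol 7.1.2.2 does. Protocol 6.5.1 and SAP 2.3 support the breadth of the definition, not the restriction.
- **That OS could come out negative**, from a screening SAE dated before randomisation. Appendix 1 (14.1.4.5.1) says time-to-event variables can never be negative. The gap is a missing rule, not a negative result.
- **That the reported primary PFS result was affected.** The SAP supplied is for the final CSR. The plan used for the primary analysis is not among the documents, so its handling of such patients is unknown.

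**Conclusion.** Minor, and wrong as written. The screen-failure definition and its data restriction, read literally, contradict the all-randomised FAS and the follow-up rules. If they were obeyed, PFS would be censored at day 1, and OS would normally have no censoring date on or after randomisation.

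The practical effect is probably negligible. It needs a site to follow 7.1.2.2 over the follow-up sections, and it needs such patients to exist, which the documents do not show. The figures rest on an assumed 2 to 5 patients and on the exponential model in protocol 10.6, which already allows for 10% loss (16 of 160). The study estimates a hazard ratio without a test, so no error rate is at stake. The effect on OS precision is not quantified here: the documents state no final cut-off date, and the primary cut-off of 19 May 2020 makes the planned accrual calendar doubtful.

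**What to change.** - **Protocol 7.1.2.2 and SAP 2.3:** limit the term screen failure, and in 7.1.2.2 the no-other-data rule, to patients who consent but are not randomised. Align protocol 6.5.1 and 7.1.6.2, so that randomised, never-dosed patients follow the existing tumour and survival schedules.
- **SAP 2.1.9:** add the randomisation date as the fallback, and as the earliest allowed last contact date for OS. This gives a duration of 1 day, as Appendix 1 already does for PFS.
- **Final CSR:** state the number of randomised, never-dosed patients by arm (FAS count minus Safety Set count) and how each was censored for PFS and OS. If there are none, one sentence closes the matter.

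The cost is wording in three protocol sections and one SAP section, one added line in SAP 2.1.9 and one statement in the report. No visit or procedure is added. Rewording the protocol cannot recover scans that were not done, so for data already collected the SAP line and the CSR statement are the useful parts.

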#### **7.1.2.3 Patient demographics and other baseline characteristics**

The following patient demographics and baseline characteristics will be collected on the eCRF:

- ER and HER2 status
- Demography including year of birth, race and ethnicity
- Height, weight (See [Section 7.2.2.3](#))
- Diagnosis and extent of cancer (including staging, histology/cytology and sites of disease at study entry)
- Medical history (e.g., important medical, surgical, and allergic conditions from the patient's medical history which could have an impact on the patient's evaluation) / current medical conditions (e.g., all relevant current medical conditions which are present at the time of signing informed consent). Ongoing medical conditions, symptoms and disease which are recorded on the Medical History eCRF should include the toxicity grade.
- Prior and concomitant medications
- Prior anticancer therapy (surgery, medication, radiotherapy); specifically, for prior anticancer therapy the following data will be collected: start and end date of therapy, setting (neo-adjuvant, adjuvant, metastatic), best response and reason for discontinuation of therapy.
- Physical Examination (See [Section 7.2.2.1](#))
- Vital signs including blood pressure and pulse (See [Section 7.2.2.2](#))
- ECOG performance status (See [Section 7.2.2.4](#))

- ECG (See [Section 7.2.2.5.3](#))
- Tumor evaluation (See [Section 7.2.1](#))
- Laboratory evaluations (e.g., hematology, coagulation, biochemistry, fasting serum lipid profile/ urinalysis) (See [Section 7.2.2.5](#))
- Hepatitis B serologic markers and viral load: HBV-DNA HBsAg, HBcAb, and HBsAb.
- The patients listed in [Section 6.3.2.3](#) should be tested for HCV RNA. If the patient is already known to have a chronic infection with HBV or HCV and is taking anti-HBV medication, the site does not have to wait for the screening HBV or HCV results prior to the first dose of the study treatment.
- Pulmonary function tests (PFTs) can be performed at screening or Treatment Day 1 (prior to administration of the study treatment) and during the trial if clinically indicated and if warranted to exclude or manage non-infection pneumonitis. Chest CT scans also be considered and can be used for exclude or manage non-infectious pneumonitis.

### **7.1.3 Treatment period**

Patients will be randomized to one of the two treatment arms (everolimus plus exemestane arm or placebo plus exemestane arm) within 7 days before Cycle 1 Day 1. Randomization will be stratified according to visceral disease status and sensitivity to prior hormonal therapy status. Patients will receive treatment until disease progression, unacceptable toxicity, death, or discontinuation from the study treatment due to any other reason.

